8.4. Duration of participant participation

Each participant will participate in the study for up to approximately 16 months.

A placebo controlled clinical trial investigating the safety and immunogenicity of GBS6 in pregnant women with and without human immunodeficiency virus (HIV) infection and their infants

Protocol Version 5.0, Dated 01/02/2023

Protocol Version/date 5.0,01/02/2023
R&D Protocol Code Number:
Page:44

8.5. Temporary Delay Criteria

The following conditions are temporary or self-limiting and a participant may be vaccinated once the condition(s) has/have resolved and no other exclusion criteria are met.

Criteria for temporarily delaying vaccine administration

- Current febrile illness (body temperature $\geq 38^{\circ}\text{C}$ [$\geq 100.4^{\circ}\text{F}$]) or other acute illness within 48 hours before investigational product administration.
- Receipt of any inactivated vaccine in the 14 days and any live vaccine within the 28 days before investigational product administration.
- Receipt of short term (<14 days) systemic corticosteroids. Investigational product administration should be delayed until systemic corticosteroid use has been discontinued for at least 30 days. Inhaled/nebulised, intraarticular, intra-bursal, or topical (skin or eyes) corticosteroids are permitted.

8.6. Discontinuation/withdrawal of participants

A study participant will be discontinued from participation in the study if:

- (i) Any medical condition or situation occurs such that continued participation in the study would not be in the best interest of the participant.
- (ii) Laboratory-confirmed documented GBS infection in this pregnancy.

For further details on participant's premature termination see corresponding section below.

Participants are free to withdraw from the study at any time without giving a reason.

Any data collected up to the point of withdrawal will continue to be used in the study analyses unless specifically requested by the participant.

A placebo controlled clinical trial investigating the safety and immunogenicity of GBS6 in pregnant women with and without human immunodeficiency virus (HIV) infection and their infants

Protocol Version 5.0, Dated 01/02/2023

Protocol Version/date 5.0,01/02/2023
R&D Protocol Code Number:
Page:45

8.7. Study stopping rules

Safety will be evaluated according to the stopping rules defined below. Stopping rules will be in effect and apply as detailed below to subjects enrolled in the study and will apply only to GBS6 vaccinated subjects. Diary data confirmed to be entered by the subject in error will not contribute toward a stopping rule.

If it is suspected that a stopping rule has been met based on blinded safety assessment, the sponsor's designated unblinded personnel (and their backup designees) will seek to verify whether a stopping rule has been met based on unblinded randomization information.

During this verification process, the investigational site will be instructed by the sponsor not to administer any further investigational product. If the unblinded sponsor personnel determine that a stopping rule has not been met, then the sponsor will notify investigational sites that administration of the investigational product may continue according to the clinical trial protocol.

In the event that the unblinded sponsor personnel confirm that a stopping rule is met, enrollment and administration of the investigational product will not continue until the DSMB has reviewed all safety data and provided recommendations to the study team. The School of Medicine Research and Ethics Committee (SOMREC), Uganda National Council for Science and Technology (UNCST), national drug authority (NDA) and the sponsor will be notified of study hold.

If, after the safety review by the DSMB, it is appropriate to restart the trial without a protocol amendment, SOMREC, UNCST & NDA will be notified and the study restarted, however if the DSMB recommends a protocol amendment the study principal Investigator will notify SOMREC, UNCST & NDA of the decision by the DSMB. The protocol amendment will be submitted to the SOMREC, Uganda National Council for Science and Technology (UNCST) and

A placebo controlled clinical trial investigating the safety and Immunogenicity of GBS6 in pregnant women with and without human immunodeficiency virus (HIV) infection and their infants

Protocol Version 5.0, Dated 01/02/2023

Protocol Version/date 5.0,01/02/2023
R&D Protocol Code Number:
Page:46

national drug authority (NDA) for approval. The trial will not restart until the amendment has been approved by the NDA, UNCST and SOMREC.

Although enrollment and vaccination activities will stop until DSMB review is complete and the issue is resolved, all other routine study conduct activities such as ongoing data entry, reporting of AEs, subject e-diary completion, subject follow-up including blood draws, etc, must continue during this time.

A stopping rule will be considered to have been met if any of the following occur:

- a) If any GBS6 vaccinated subject develops an SAE within 30 days following vaccination for which there is no other clear attributable cause, or if the investigator determines that the SAE is related to vaccination.
- b) If any GBS6 vaccinated subject experiences a prompted local reaction or systemic event considered related to vaccination that results in an emergency room visit, or a local equivalent to this type of visit, or has local necrosis or exfoliative dermatitis (Grade 4 event) within 7 days following vaccination, or a Grade 4 laboratory abnormality at or before the 2-week postvaccination visit.
- c) If more than 6 GBS6 vaccinated subjects experience the same Grade 4 local reaction or systemic event within 7 days following vaccination, not attributable to any other cause, including:
 - i. Local redness
 - ii. Local swelling
 - iii. Local pain
 - iv. Headache
 - v. Fatigue
 - vi. Joint pain
 - vii. Muscle pain
 - viii. Nausea/vomiting

A placebo controlled clinical trial investigating the safety and immunogenicity of GBS6 in pregnant women with and without human immunodeficiency virus (HIV) infection and their infants

ix. Diarrhea

- d) If more than 2 GBS6 vaccinated subjects experience the same or similar Grade 3 or 4 unsolicited AE within 7 days following vaccination, or laboratory abnormality at or before the 2-week postvaccination visit, not attributable to any other cause.
- e) If more than 2 GBS6 vaccinated subjects experience fever greater than 39.0°C (greater than 102.1°F) for more than 2 consecutive days within 7 days following vaccination, for which there is no other clear attributable cause.
- f) If any GBS6 vaccinated subject experiences a confirmed fever >40.0°C (>104.0°F) for 1 daily measurement within 7 days following vaccination, for which there is no other clear attributable cause.
- g) If more than 2 GBS6 vaccinated subjects experience premature labor or premature rupture of membranes within 14 days after vaccination.
- h) If any GBS6 vaccinated subject experiences severe vaginal bleeding (eg, partial abruption), severe preeclampsia, eclampsia, HELLP (hemolysis, elevated liver enzymes, and low platelet count) syndrome, or life threatening sequelae of preeclampsia (eg, pulmonary edema), stillbirth, or fetal loss within 14 days after vaccination.
- i) If any GBS6 vaccinated subject develops an SAE during participation in the study following vaccination for which the investigator determines that the SAE is related to vaccination.

A placebo controlled clinical trial investigating the safety and immunogenicity of GBS6 in pregnant women with and without human immunodeficiency virus (HIV) infection and their infants

Protocol Version 5.0, Dated 01/02/2023

Protocol Version/date 5.0,01/02/2023
R&D Protocol Code Number:
Page:48

9. Methods

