6.2 Study populations

Safety population

A safety population will be defined separately for, maternal participants and their infant participants. For the safety analyses, maternal participants will be analysed according to the investigational product received and infant participants will be analysed according to the investigational product their mothers (maternal participants) received.

- Maternal participants: All maternal participants receiving a dose of GBS6 or placebo will be included in the safety population.
- Infant participants: All infant participants who are enrolled in the study will be included in the safety population.

Immunogenicity population

Two populations will be defined separately for maternal participants and their infant participants: evaluable immunogenicity population and modified intent-to-treat (mITT) populations. Immunogenicity data will be analysed separately for maternal participants and their infant participants.

For the immunogenicity analyses, maternal participants will be analysed according to the investigational product received for the evaluable immunogenicity population and the investigational product as randomised for the mITT population. Infant participants will be analysed according to the investigational product received by their mothers (maternal participants) for the evaluable immunogenicity population and the investigational product assigned to

A placebo controlled clinical trial investigating the safety and immunogenicity of GBS6 in pregnant women with and without human immunodeficiency virus (HIV) infection and their infants

Protocol Version 5.0, Dated 01/02/2023

Protocol Version/date 5.0,01/02/2023
R&D Protocol Code Number:
Page:32

their mothers (maternal participants) for the mITT population. The evaluable immunogenicity population is considered to be the primary population for the immunogenicity analyses.

- Maternal participants

To be included in the evaluable immunogenicity population, the maternal participant must have been eligible for the study, have received GBS6 or placebo as randomised, have had blood drawn within the specified time frames, have at least one valid and determinate assay result for the proposed analysis, and have no other major protocol violations. To be included in the mITT population, the maternal participant must be randomised and have at least one valid and determinate assay result related to the proposed analysis.

- Infant participants

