Visit 4 (Delivery): 1x10mls cord blood drawn for immunogenicity assessment, dried blood spot card collection and nasal/rectal swab to determine GBS status.

Visit 5 (1 week post-delivery): telephone call to check on health

Visit 6 (6-weeks post-delivery): Infant ~5mls blood at 6 weeks and nasal/rectal swab to determine GBS status.

Visit 7 (18-weeks post-delivery): Infant ~5mls blood and nasal/rectal swab to determine GBS status.

Visit 8 (6 months post-delivery): telephone call to check on health

Visit 9 (12-months post-delivery): Infant ~5mls blood at 12 months.

A placebo controlled clinical trial investigating the safety and immunogenicity of GBS6 in pregnant women with and without human immunodeficiency virus (HIV) infection and their infants

Protocol Version 5.0, Dated 01/02/2023

Protocol Version/date 5.0,01/02/2023

R&D Protocol Code Number:

Page:52

10. Trial Investigational Product

All maternal participants will receive either a placebo or GBS6. This vaccine will be given at the time period assigned by randomisation. **No vaccine will be given as part of the study at ≤ 26 6/7 Gestational weeks as per inclusion/exclusion criteria.**

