14.1. Requirements

For all AEs, the investigator will pursue and obtain information adequate both to determine the outcome of the AE and to assess whether it meets the criteria for classification as a serious adverse event (SAE) requiring immediate notification to the Makerere University School of Medicine Research and Ethics Committee (SOMREC), Data and Safety Monitoring Board (DSMB), sponsor (SGUL), Uganda National Council for Science and Technology (UNCST) and Pfizer Safety. SAEs shall be reported for the entire duration of the study. Should an investigator be made aware of any SAE occurring any time after the active reporting period, this will be promptly reported.

The table below summarises the requirements for recording safety events on the CRF and for reporting safety events on the Clinical Trial (CT) Serious Adverse Event (SAE) Report Form. These requirements are delineated for the following events: SAEs; non-serious AEs; and occupational exposure.

A placebo controlled clinical trial investigating the safety and immunogenicity of GBSG in pregnant women with and without human immunodeficiency virus (HIV) infection and their infants

Protocol Version 4.0, Dated 11/05/2022

ProtocolVersion/date 5.0, 01/02/2023
R&D Protocol/CodeNumber:
Page:95

Safety Event	Recorded on the CRF	Reported on the CT SAE Report Form Within 24 Hours of Awareness
Maternal and Infant participants		
SAE	All	All
Nonserious AE	All	None
Exposure to the investigational product under study via occupational exposure	None	Occupational exposure (regardless of whether associated with an AE)

The PI/Designee will coordinate the safety monitoring and reporting in the study. SAEs will be reported to SOMREC following local law and requirements. SAEs will be reported to the

A placebo controlled clinical trial investigating the safety and immunogenicity of GBS6 in pregnant women with and without human immunodeficiency virus (HIV) infection and their infants

Protocol Version 4.0, Dated 11/05/2022

ProtocolVersion/date 5.0, 01/02/2023
R&D ProtocolCodeNumber:
Page:96

DSMB as required as well. A detailed description of DSMB functions and responsibilities and guidelines on the transmission flow of SAEs is provided in the DSMB charter. Notification of SAE to concerned National Regulatory Authorities will follow national law requirements. The table below summarizes SAE reporting timelines.

SAE reporting timelines

Reported To	Reported By	Timeline

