14.5.3 Recording non-serious AEs and SAEs on the CRF

All AEs/SAEs occurring in a participant during the active collection period are recorded in the CRF.

Follow up by the investigator may be required until the event or its sequelae resolve or stabilise at a level acceptable to the investigator, the sponsor and regulatory authorities.

The investigator obtains general information on the pregnancy and its outcome for all study participants. The investigator will follow the pregnancy until completion (or until pregnancy termination). In the case of a live birth, the structural integrity of the neonate can be assessed at the time of birth. In the event of a termination, the reason(s) for termination

A placebo controlled clinical trial investigating the safety and immunogenicity of GBS6 in pregnant women with and without human immunodeficiency virus (HIV) infection and their infants

Protocol Version 4.0, Dated 11/05/2022

ProtocolVersion/date 5.0, 01/02/2023
R&D ProtocolCodeNumber:
Page:99

should be specified and, if clinically possible, the structural integrity of the terminated fetus should be assessed by gross visual inspection (unless pre-procedure test findings are conclusive for a congenital anomaly and the findings are reported).

If the outcome of the pregnancy meets the criteria for an SAE (i.e., ectopic pregnancy, spontaneous abortion, including miscarriage and missed abortion, intrauterine fetal demise, neonatal death [defined as those deaths that occur within 1 month of birth], or congenital anomaly [in a live-born baby, a terminated fetus, an intrauterine fetal demise, or a neonatal death]), the investigator should record this information in the CRF. In addition, infant deaths after 1 month of age should be recorded in the CRF as SAEs.

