If the outcome of the pregnancy meets the criteria for an SAE (i.e., ectopic pregnancy, spontaneous abortion, including miscarriage and missed abortion, intrauterine fetal demise, neonatal death [defined as those deaths that occur within 1 month of birth], or congenital anomaly [defined as structural or functional anomalies (e.g., metabolic disorders) that occur during intrauterine life and can be identified prenatally, at birth or later in life]). These SAEs can occur in a live-born baby, a terminated fetus, an intrauterine fetal demise, or a neonatal death; the investigator should follow the procedures for reporting SAEs and record this information in the CRF. In addition, any infant death after 1 month of age should be reported as an SAE if the investigator assesses the infant death as related or possibly related to exposure to the investigational product.

Further follow-up may be requested by the sponsor and will be handled on a case-by-case basis (e.g., follow-up on preterm infant participants to identify developmental delays). SAEs occurring in a participant after the active collection period has ended are reported if the investigator becomes aware of them; at a minimum, all SAEs that the investigator believes have at least a reasonable possibility of being related to investigational product must be reported.

A placebo controlled clinical trial investigating the safety and immunogenicity of GBS6 in pregnant women with and without human immunodeficiency virus (HIV) infection and their infants

Protocol Version 4.0, Dated 11/05/2022

ProtocolVersion/date 5.0, 01/02/2023
R&D ProtocolCodeNumber:
Page:103

The same is applied for those SAEs after the active collection period has ended should they occur to the fetus. In addition, infant deaths that occur after 12 months of age should be reported as SAEs when the investigator believes the death has at least a reasonable possibility of being related to investigational product.

Adverse events which do not fall into these categories are defined as non-serious. It should be noted that a severe adverse event need not be serious in nature and that a serious adverse event need not, by definition, be severe.

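### Section 8.7 states no pause in dosing for a vaccine-related SAE in a live-born infant that is not a pregnancy outcome, although it does for the mother

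*Protocol*

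**What the plan says.** Section 8.7 opens by stating that the stopping rules "will apply only to GBS6 vaccinated subjects". Each of rules (a) to (i) then repeats that limit. Rule (i), the only one without a time limit after the dose, reads "If any GBS6 vaccinated subject develops an SAE during participation in the study following vaccination for which the investigator determines that the SAE is related", meaning related to vaccination.

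The consequence of a suspected trigger is firm: "During this verification process, the investigational site will be instructed by the sponsor not to administer any further investigational product". If the unblinded sponsor staff confirm the trigger, enrolment and dosing stay closed until the DSMB has reviewed all safety data and made its recommendations.

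Section 10 says who is dosed: "All maternal participants will receive either a placebo or GBS6". Infants are enrolled as participants in their own right. Section 5.2 makes their safety Primary Objective 2, and infant SAEs through 12 months are part of an infant primary endpoint.

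Section 14.6 requires a causality assessment of every AE and SAE. Section 14.8 foresees the infant case directly: "any infant death after 1 month of age should be reported as an SAE if the investigator assesses the infant death as related", with a possible relation to the product counted as well.

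**The concern.** In a maternal vaccine trial the infant is one of the two people whose safety is being tested. A pause rule protects the women and fetuses who have not yet been exposed. If an infant SAE is judged related to the vaccine, the case for stopping further doses until it has been reviewed is at least as strong as for a related SAE in the mother. Read literally, 8.7 makes the pause mandatory in the second case and says nothing in the first. The protocol gives no reason for the difference. At stake is whether dosing would continue by default after such an infant event, with any hold left to someone's discretion.

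**Working it through.** This is mainly a check of wording; arithmetic is needed only to see whether an infant trigger would still have any dosing to pause.

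**1. Does the limit in 8.7 exclude infants?**
- Section 14.14.3 uses the word subject for an infant, so the limiting word in 8.7 is vaccinated.
- Section 11.4 describes infants as born from vaccinated mothers, not as vaccinated.
- Where the protocol wants to carry the mother's product over to the infant, it says so. In section 6.2, "infant participants will be analysed according to the investigational product their mothers (maternal participants) received". Section 8.7 has no such wording.

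**2. Does another rule close the gap?**
- Rule (a) covers SAEs within 30 days of the dose. Its second limb, on SAEs judged related, refers back to the same vaccinated subject.
- Rules (b) to (f) concern the vaccinated subject's reactogenicity, laboratory results, unsolicited AEs and fever.
- Rules (g) and (h) are obstetric. The only offspring outcomes named are stillbirth and fetal loss, in rule (h), within 14 days of the dose.
- No rule names a live-born infant.

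**3. Which infant events are affected?**
- *Not a pregnancy outcome* (related hospitalisation, life-threatening illness, death after 1 month): no rule applies.
- *Neonatal death and congenital anomaly*: sections 14.5.3 and 14.8 list these under the heading "If the outcome of the pregnancy meets the criteria for an SAE". Rule (h) treats stillbirth and fetal loss as things the vaccinated woman experiences. Taken together, these two events are plausibly her SAE under rule (i), or under rule (a) if within 30 days of the dose. Section 14.8 also says such SAEs can occur in a live-born baby, so the wording does not settle it.

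**4. Would an infant trigger come while dosing continues?** Inputs: planned dates October 2022 to September 2024, about 24 months (synopsis); dosing at 27 0/7 to 35 6/7 weeks; screening 2 to 14 days before the dose; last visit 365 to 385 days after delivery (schedule of activities). Assumptions: uniform accrual and birth at 40 0/7.
- Lag L from dose to birth: 280 − 251 = 29 days to 280 − 189 = 91 days.
- Participation: longest 14 + 91 + 385 = 490 days (16.1 months, matching section 8.4); shortest 2 + 29 + 365 = 396 days (13.0 months).
- Dosing period D: 24 − 16 = 8 months (244 days) to 24 − 13 = 11 months (335 days).
- Born before the last dose, (D − L)/D: (244 − 91)/244 = 62.7% to (335 − 29)/335 = 91.3%. With birth anywhere from 37 0/7 to 41 0/7 (L from 8 to 98 days), 59.8% to 97.6%.
- Past 30 days of age by the last dose, (D − L − 30)/D: 123/244 = 50.4% to 276/335 = 82.4%.
- Share of the 365-day infant follow-up that falls within dosing, (D − L)²/(2 × D × 365): 153²/(2 × 244 × 365) = 13.1% to 306²/(2 × 335 × 365) = 38.3%.

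So most infants would be born, and at least half would be past 1 month of age, before the last dose. Most infant follow-up, about 62% to 87%, comes after dosing ends, when a pause can no longer do anything.

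**The case against.** The strongest reply is that these events do not go unseen. Section 14.1 calls for immediate notification of SAEs to the ethics committee, the DSMB and the sponsor, among others. Its timeline table gives the sponsor 24 hours for every SAE and the DSMB 24 hours for fatal and life-threatening events. Two of the three examples above, death after 1 month and life-threatening illness, are therefore on the fast route. The table's 7-day limit matters only for other SUSARs, such as an unexpected related hospitalisation. The DSMB charter, which is not shown, may hold an infant trigger, and section 18.1 allows an urgent change to remove an immediate hazard. All of this stands as mitigation. None of it is a pause that this protocol requires, and a charter trigger would sit beside a scope sentence that says only.

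A reader might go further and infer that a related neonatal death or congenital anomaly would leave dosing running. The documents do not support that: rule (h) and sections 14.5.3 and 14.8 make the opposite reading plausible. Nor do they support the inference that infant SAEs escape the DSMB, or any estimate of infants harmed. The national infant and neonatal mortality rates in sections 4.2 and 4.4 are all-cause, the cohort is low-risk, and only events judged related would count.

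**Conclusion.** The gap is real but narrow. By its own wording, 8.7 attaches no pause to a vaccine-related SAE in a live-born infant that is not a pregnancy outcome, while a related SAE in the mother stops dosing at any time in the study. For neonatal death and congenital anomaly the rule needs clarifying, not reversing. The conclusion rests on the text of 8.7 and makes no claim about the charter. The overlap figures are indicative: they depend on planned dates, uniform accrual and term birth, and their upper ends need the longest dosing period and every woman dosed at 35 6/7. They show only that an infant trigger would not be empty. The gap is worth fixing because the remedy is cheap and the population is that of a primary objective.

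**What to change.** Three changes to section 8.7:

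1. Reword rule (i) along these lines: *If any GBS6 vaccinated subject, or any infant born to one, has an SAE during the study that the investigator judges related to vaccination.*
2. Extend the scope sentence to GBS6 vaccinated subjects and, for rule (i), their infants.
3. State that the pregnancy-outcome SAEs of 14.5.3 and 14.8, including neonatal death and congenital anomaly, fall under rule (i) only when judged related, and that verification uses the mother's unblinded allocation. The relatedness condition must be explicit; without it, every neonatal death or anomaly could be read as a trigger.

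The DSMB charter should be aligned. No new data are needed, since infant SAEs and their causality are already recorded. The cost is an occasional extra temporary hold. Dosing stops on suspicion, before unblinding, and section 14.6 counts a possible relation as related, so an infant from the placebo arm could also cause a short pause until verification is done. How often this would happen cannot be estimated, because the protocol gives no rate of related infant SAEs.
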